8.4.2 Dispensing

The drug will be dispensed by the pharmacist of the research pharmacies of both study sites where it will be collected by study personnel. The Research pharmacy at each site will encapsulate study drug and placebo so that all study pills will look identical. Only the research pharmacist at each site will know the true identify of the study pills for each participant.

8.4.3 Administration Instructions

Following FDA packaging information, ezogabine will be given orally according to the titration and taper schedule described above. Participants will be instructed to swallow the whole tablet, with or without food. At every study visits the subject will receive the study drug in a drug case labeled with the required FDA warning statement, the protocol number, a treatment number, the name of the Sponsor, and directions for patient use and storage. The dosage will be prescribed by the PI or the Study Doctor, according to the period of the study (titration, treatment, and taper period), tolerability showed by the participant and length from the subsequent visits.

8.4.4 Storage

Study drug should be stored by the study site at controlled room temperature, 15 to 30°C (59 to 86°F). If the temperature of study drug storage in the clinic/pharmacy exceeds or falls below this range, this should be reported to the PI or designee and captured as a deviation. Subjects will be instructed to store the medication in original packaging (protected from light) at room temperature.

8.5 Study Medication Accountability

An accurate and current accounting of the dispensing of study drug for each subject will be maintained on an ongoing basis by a member of the study site staff. The number of study drug dispensed will be recorded on the Investigational Drug Accountability Record.

8.6 Measures of Treatment Compliance

Subsequent to randomization, study participants are provided with study drug or placebo in identical packaging and sufficient medication to reach the next visit is dispensed (plus a few extra days supply to account for scheduling and related issues). Adherence to study medication will be measured throughout the study using pill count, patient diary, subject report, and drug plasmatic levels. Subjects will be asked to keep a patient diary noting the date and time they take the study drug and any adverse effects. They will be asked to bring their patient diary to each study visit along with all used and unused study drug containers. Compliance monitoring by pill counting will occur at each study visit: pills will be returned for pill counting in the study drug containers. A study team member will count the number of returned pills and record the number on the "Pill tracking log". Venous blood samples will be collected for determination of plasmatic ezogabine concentrations at the time point

specified and will be summarized by visit. Drug concentrations will be used to determine protocol adherence, inclusion in the planned per-protocol analysis and to examine PK and PD relationships.

9 STUDY PROCEDURES AND GUIDELINES

A Schedule of Events representing the required testing procedures to be performed for the duration of the study is summarized in Table 2.

Prior to conducting any study-related activities, written informed consent and the Health Insurance Portability and Accountability Act (HIPAA) authorization must be signed and dated by the subject.

9.1 Clinical Assessments

9.1.1 Concomitant Medications

All concomitant medication and concurrent therapies will be documented at screening (V-1) and at each study visit, and at early termination when possible. Dose, route, unit frequency of administration, and indication for administration and dates of medication will be captured using the Concomitant Medication Log case report form.

9.1.2 Demographics

Demographic information (date of birth, gender, race) will be recorded at screening (V-1). The case report forms used to capture this information include the Demographics Form and the Edinburg Handedness Inventory.

9.1.3 Medical History

Relevant medical history, including history of current disease, other pertinent history, and information regarding underlying diseases will be recorded at screening (V-1). Case report forms used to record the medical history include the Medical History Form, Family Psychiatric History Form, and the Anti-Depressant Treatment History Form (ATHF).

9.1.4 Physical Examination

A complete physical examination will be performed by qualified staff (MD, NP, RN, or PA) at screening (V-1) and at study end (V6). New abnormal physical exam findings must be documented and will be followed by a physician or other qualified staff at the next scheduled visit. According to FDA recommendation, all study participants will undergo a complete ophthalmological exam at screening and at study end by a study ophthalmologist, to include the following procedures: Visual acuity, Color plates, Amsler grid, Visual field test, Dilated fundus exam, Fundus photography, and Ocular coherence tomography (OCT) of the macula. For more information about the measures to minimize participants risks related to the study drug and participation in the clinical trial please refer to sections 2.1 "Risk/Benefit

Assessment” and 5.3 “Safety evaluation”. This is documented on the Physical Exam case report form.

9.1.5 Vital Signs

Body temperature, blood pressure, pulse and respirations will be performed after resting for 5 minutes at screening (V-1) and at study end (V6). This is documented on the Vitals case report form.

9.1.6 Other clinical procedures

Screening and baseline procedures

Structured Clinical Interview for DSM-5 (SCID-5). The Structured Clinical Interview for DSM-5 (First et al., 2015) is the most recent version of the SCID and is the first update since the SCID-IV-TR (First et al., 2002). The SCID-5 is a semi-structured interview guide for making DSM-5 diagnoses. It includes an overview to obtain information about demographics, work history, chief complaint, history of present illness, past history, treatment history, and current functioning. The main body of SCID-5 includes 9 modules that are designed to diagnose 51 mental illnesses in all. During the study screening period, the SCID-5 will be administered by a trained study team member who has completed SCID-5-RV training and who is familiar with the DSM-5 classification and diagnostic criteria. The current study will utilize the most comprehensive version of the SCID-5, the SCID-5-Research Version (RV), which contains more disorders than the Clinician Version and includes all of the relevant subtypes, severity, and course specifiers. An important feature of the SCID-5-RV is its customizability, allowing the instrument to be tailored to meet the requirements of a particular study. The SCID-5-RV comes in a standard "core" configuration that includes the disorders most researchers are likely to assess routinely for most studies, as well as in an “enhanced” configuration that includes a number of optional disorders, in addition to the disorders from the "core" configuration.

Snaith-Hamilton Pleasure Scale (SHAPS): The SHAPS (Snaith et al., 1995) is a well-validated 14-item self-report questionnaire commonly used to assess anhedonia. Each item on the SHAPS is worded so that higher scores indicate greater pleasure capacity. A total score can be derived by summing the responses to each item. Items answered with “strongly agree” are coded as “1”, while a “strongly disagree” response was assigned a score of “4.” Total scores on the SHAPS can range from 14 to 56, with higher scores corresponding to higher levels of anhedonia. This scale provides our primary measure of anhedonia in the study.

Clinical Global Impression - Severity (CGI-S): this is a widely administered clinician rated global measure of subject overall illness severity (Guy, 1976). Subjects are rated on a 1-7 scale where 1 corresponds to “Normal, Not at All Ill”, 2 is “Borderline Mentally Ill”, the anchor for 3 is “Mildly Ill”, the anchor for 4 is “Moderately Ill”, 5 is “Markedly Ill”, 6 is “Severely Ill”, and 7 is “Among the Most Extremely Ill Patients”. It will be administered at screening and at all study visits.

World Health Organization Disability Assessment Schedule 2.0 (WHODAS 2.0): the WHODAS 2.0 (World Health Organization, 2012) is a 12-item generic assessment instrument that measures investigating the level of functioning in six domains: Cognition, Mobility, Self-care, Getting along, Life activities, and Participation. For all six domains, WHODAS 2.0 provides a profile and a summary measure of functioning and disability that is reliable and applicable across cultures, in all adult populations. WHODAS 2.0 has proven useful for assessing health and disability levels in the general population and in specific groups (e.g. people with a range of different mental and physical conditions).

Mini–Mental State Examination (MMSE): The MMSE (Folstein et al., 1975) is a 30-point questionnaire that is used extensively in clinical and research settings to measure cognitive impairment. It is commonly used to screen for dementia, to estimate the severity and progression of cognitive impairment and to follow the course of cognitive changes in an individual over time. Administration of the test takes between 5 and 10 minutes and examines functions including registration, attention and calculation, recall, language, ability to follow simple commands and orientation. The MMSE will be used in the current study in order to exclude for cognitive impairment at screening.

Primary Outcome Measure: Neuroimaging Methods

fMRI Task Description. The current proposal will implement a variation of the monetary incentive delay (MID) task, the incentive flanker task (IFT). The IFT incorporates a longer mean cue time, jittered cue time, and catch trials, all features that facilitate differentiation between reward expectancy and reward responsiveness (Stern et al., 2011), though data should be comparable to that obtained from the MID for purposes of comparison (thereby facilitating the NIH common data elements initiative). We have demonstrated in our laboratory that the IFT robustly engages the cortico-striatal reward circuit. During the flanker conflict portion of the task, participants are instructed to press the left response button for target letters S/K and the right response button for letters H/C (letter assignment is counterbalanced across subjects). Target letters are flanked by letters representing same or different button presses. Cues presented prior to letter stimuli (2-6 s) designate the monetary value for each trial: (1) “gain” cues indicate that subjects earn 50 cents with a correct response (and fail to gain with an error); (2) “loss” cues indicate that subjects can avoid a loss of 50 cents with a correct response (and lose money with an error); (3) “neutral” cues indicate that no money is at stake. Two-thirds of all cues will be followed by the letter stimuli. Immediately after the response, outcome feedback is presented for 2 s, followed by a blank inter-trial interval (ITI) for 2–6s before the next trial begins with a new cue. One-third of cues will be followed by a blank screen for 2s (“catch” trials), which will break co-linearity between the cue and feedback, allowing differentiation of brain activity related to expectancy and feedback response despite the slow hemodynamic response of the Blood-Oxygen-Level-Dependent (BOLD) signal. Even though BOLD signals to the button press response and outcome are not distinguishable in the current paradigm, comparisons between gain, loss, and null outcomes will subtract out brain activity related to motor responses occurring in each condition.

fMRI Task Analysis. Prior to analyzing imaging data, task behavioral data including reaction time (RT) and accuracy in response to flanker stimuli will be analyzed using ANCOVAs (including site, and any potential confounds) to examine main effects and interactions of treatment condition and cue type on reaction time and accuracy. fMRI data will undergo preprocessing using a combination of AFNI, FSL, and Advanced Normalization Tools (ANTs), including despiking, motion correction, alignment to anatomical image (using boundary-based registration), intensity normalization, smoothing (FWHM = 5mm), and warping to standard space. Motion and intensity outliers will be regressed out the data.

Following preprocessing, we will first conduct subject-level (also called ‘first-level’) analyses. As is the norm in the field, subject-level analyses conduct multiple linear regressions for each subject whereby the BOLD signal is predicted from a series of categorical regressors specifying the presence or absence of the conditions of interest across the full timeseries. As an example, in a trial where a cue is shown for 4 seconds followed by an outcome for two seconds, followed by another cue for 4 seconds, the cue regressor would be coded “1” (present) for the first and last 4 timepoints (in seconds) and “0” (absent) for the 2 middle timepoints where the outcome was shown. For each subject, regressions are performed within a standardized neuroimaging analysis software (such as Statistical Parametric Mapping, FSL, or AFNI), producing a single beta weight for each regressor reflecting the relationship between the presence/absence of condition of interest and BOLD signal at each voxel in the brain. For all analyses, the predicted BOLD signal is convolved with a standard hemodynamic response function (hrf) to model the slow rise and fall of the hemodynamic response in the brain. For each subject, the beta weights are then linearly combined to create contrasts (gain > neutral cue contrast, the primary contrast of interest for this study, is the beta weight for gain cue minus beta weight for neutral cue). This contrast represents the mental construct of reward anticipation.

Group level analysis is described in Section 16, Statistical Methods and Consideration.

Resting State fMRI (R-fMRI). Approximately 10 minutes worth of resting state fMRI data will be collected at both sites, pre- and post-treatment. Participants will be instructed to rest, eyes open and fixed on a central fixation cross, and to try to remain as still as possible. R-fMRI data will be examined primarily as an exploratory aim and additionally contributes to the common data element initiative. As there are a number of serious, potential confounds to the analysis of R-fMRI, advanced processing and analytic methods will be employed, including the use of robust artifact detection and removal (Pruim et al., 2015). We will conduct targeted analysis to explore whether treatment alters connectivity and network patterns with known abnormalities and that are specifically impacted by our treatment (e.g., fronto-striatal connectivity implicated in reward; see Heller et al., 2013).

Please see **MRI Procedures Appendix** for details regarding image acquisition, data transfer, processing, and multi-site data quality assurance.

Secondary Outcomes and Safety Measures

Clinical Assessments

Temporal Experience of Pleasure Scale (TEPS): The TEPS is an 18-item self-report measurement of anticipatory (10 items) and consummatory (eight items) components of anhedonia which consists of a series of statements that must be rated according to how accurate they are for the individual (Gard et al. 2006). The scale differentiates the role of anticipatory pleasure ('wanting') from consummatory pleasure ('liking'). This scale provides a measure of anhedonia and will be used in exploratory analyses.

Anticipatory and Consummatory Interpersonal Pleasure Scale (ACIPS): The ACIPS (Gooding & Pflum, 2014) is a measure specifically designed to assess hedonic capacity for social and interpersonal pleasure. Given the importance of social rewards for normal human experience, and for depressive psychopathology, we include the recently developed ACIPS in our current study as an exploratory measure. The ACIPS was designed to assess one's ability to experience pleasure in the interpersonal domain. It is a 17-item self-report measure that consists of seven anticipatory and 10 consummatory items. The ACIPS is scored on a Likert scale, ranging from 1 (very false for me) to 6 (very true for me). The format is therefore quite similar to that of the TEPS. Validation studies show good internal consistency, convergent and discriminant validity, and good test-retest stability.

Specific Loss of Interest and Pleasure Scale (SLIPS): The SLIPS (Winer et al., 2014) is a recently developed and validated measure of anhedonia that is tailored to detect recent changes in anhedonia. Many scales, including the SHAPS and the TEPS, appear tailored more towards assaying trait-like features related to anhedonia. The scale consists of 23 items; items range from 0-3 to indicate the degree of change in interest or pleasure from a specific experience, relative to the past. Validation studies show that the SLIPS is internally consistent, converged with existing state measures of anhedonia and depression, and diverged from general measures of affect and trait anticipatory and consummatory pleasure. The SLIPS predicted recent changes in anhedonia independent of existing measures. Moreover, in respondents reporting moderate or severe symptoms of depression, only the SLIPS was associated with recent changes in anhedonia.

The Quick Inventory of Depressive Symptomatology, Self-Report (QIDS-SR): The QIDS (Rush et al. 2003) is a 16-item self-rated instrument designed to assess the severity of depressive symptoms. The 16 items cover the nine symptom domains of major depression, and are rated on a scale of 0-3. Total score ranges from 0 to 27, with ranges of 0-5 (normal), 6-10 (mild), 11-15 (moderate), 16-20 (moderate to severe), and 21+ (severe).

Montgomery-Asberg Depression Rating Scale (MADRS) (Montgomery & Asberg, 1979): this is a 10-item instrument used for the evaluation of depressive symptoms in adults and for the assessment of any changes to those symptoms. Each of the 10 items is rated on a scale of 0 to 6, with differing descriptors for each item. These individual item scores are added

together to form a total score, which can range between 0 and 60 points. The MADRS provides a measure of the overall level of depression.

The Mood and Anxiety Symptoms Questionnaire (MASQ) (Wardenaar et al., 2010): This is a 30-item self-report questionnaire, designed to measure dimensions of depression and anxiety and has been validated in both clinical and non-clinical samples. The MASQ provides three factors with good construct validity: negative affect, positive affect and somatic arousal. The scale will be used in the current study to explore changes in the dimensions of depression and anxiety.

Clinical Global Impression - Improvement (CGI-I): this is a widely administered clinician rated global measure of the degree of improvement from the initial assessment in subject overall illness severity. Subjects are rated on a 1-7 scale where 1 corresponds to “Very Much Improved”, 2 is “Much Improved”, the anchor for 3 is “Minimally Improved”, the anchor for 4 is “No Change”, 5 is “Minimally Worse”, 6 is “Much Worse”, and 7 is “Very Much Worse”. It will be administered at all subject visits. During the course of the trial subjects for whom the CGI-I is greater than 5 will be removed from the study and appropriate care given, for safety purposes.

Columbia-Suicide Severity Rating Scale (C-SSRS): The Columbia-Suicide Severity Rating Scale (C-SSRS) (Posner et al., 2007) is a comprehensive, semi-structured interview that uniquely measures the full spectrum of suicidality including passive and active suicidal ideation, suicidal intent as well as suicidal behaviors. Subjects will be assessed at every visit with the CSSRS by a qualified rater. Study participants will meet with a study physician at each study visit, which will include a review of the C-SSRS. Any subject with an increase in suicidality and all those subjects found to have a plan or intent will undergo thorough assessment by the study psychiatrist. If, at any point during the clinical trial, a participants will be assessed by the study physician with a suicidal ideation with any intent or plan, as measured by a C-SSRS score of greater than 3 during the past week and with either a GCI-S score ≥ 6 (indicating extreme illness severity) or a CGI-I score ≥ 6 (indicating an extreme worseness of the symptoms), the site PI, or his designee, will conduct a safety review to determine the appropriate course of action including whether acute intervention is needed and whether it is in the best interests of the subject to continue in the study. For more details regarding the safety review procedures, please refer to section 5.3 “Safety evaluation”.

Behavioral assessment

Probabilistic Reward Task (PRT): This 25-min task is presented on a 17” PC monitor using E-Prime (version 1.1; Psychology Software Tools, Inc, Pittsburgh, PA). Stimuli consist of simple cartoon faces presented in the center of the monitor. At the beginning of the trial, the face has no mouth. After a given delay, either a straight mouth of 11.5 mm (“short mouth”) or 13 mm (“long mouth”) is presented for 100 ms. On each trial, subjects are instructed to press an appropriate button to decide whether a long or small mouth had been presented. Unbeknownst to subjects, correct identification of one stimulus (the “rich stimulus”) is

rewarded three times more frequently (“Correct! You won 20 cents”) than the other (“lean”) stimulus. In healthy controls, this reinforcement schedule leads to a response bias (i.e., a preference for the more frequently rewarded stimulus). The task consists of three 100-trial blocks, and the degree of response bias toward the more frequently reinforced stimulus is used for operationalizing sensitivity to reward. An index of reward learning across the task is then computed by subtracting the total response bias in the first block from the total response bias in the last block. Stimulus exposure (100 ms) and the difference between mouth sizes (11.5 vs. 13 mm) are identical to those in prior studies using this paradigm (Pizzagalli et al., 2005, Pizzagalli et al., 2008, Vrieze et al., 2013) and were selected to achieve optimal psychometric properties (e.g., overall hit rates of 75-85%).

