Antiepileptic drugs (AEDs), including ezogabine, have been found to increase the risk of suicidal thoughts or behavior in pooled analyses. Pooled analyses of 199 placebo-controlled clinical trials (mono- and adjunctive-therapy) of 11 different AEDs showed that patients randomized to one of the AEDs had approximately twice the risk (adjusted relative risk 1.8, 95% confidence interval [CI]: 1.2, 2.7) of suicidal thinking or behavior compared to patients randomized to placebo. In these trials, which had a median treatment duration of 12 weeks, the estimated incidence of suicidal behavior or ideation among 27,863 AED-treated patients was 0.43% compared to 0.24% among 16,029 placebo-treated patients, representing an increase of approximately 1 case of suicidal thinking or behavior for every 530 patients treated. There were 4 suicides in drug-treated patients in the trials and none in placebo-treated patients, but the number is too small to allow any conclusion about drug effect on suicide. Suicide ideation and behavior will be monitored during the length of the study through clinical assessments at screening and exit visits, and weekly during the treatment period. The Columbia Suicide Severity Rating Scale (C-SSRS) will also be conducted at each study visit to monitor suicidal ideation and behavior. If, at any point during the clinical trial, a participant will be assessed with a suicidal ideation with any intent or plan, as measured by a C-SSRS score of greater than 3 during the past week and/or with a Global Clinical Impression – Severity Scale (GCI-S) score ≥ 6 (indicating extreme illness severity) or a Global Clinical Impression – Improvement Scale (CGI-I) score ≥ 6 (indicating an extreme worseness of the symptoms), a safety review will be performed by the site PI, or his designee, to determine the appropriate course of action including whether acute intervention is needed and whether it is in the best interests of the subject to continue in the study. For more information, refer to paragraphs 5.3 “Safety evaluations” and section 9 “Study Procedures and Guidelines”.

Other Adverse Effects:

Other side effects include urinary retention, neuropsychiatric symptoms (confusional state, psychotic symptoms, and hallucinations) and withdrawal seizures. To protect participants from these possible side effects the following actions will be completed:

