5.3 Safety Evaluations

Safety will be monitored by the evaluation of potential adverse events, clinical laboratory test results, vital signs measurements, physical examination, ECG and ophthalmological findings. Our safety evaluations include frequency and severity of observed adverse events over the study treatment period. The frequency and severity of adverse events will be compared between the treatment conditions. For a complete discuss of risks associated with the study drug, please see section 2.1 “Risk/Benefit Assessment”. For a complete discussion of study procedures, please see section 9 “Study Procedures and Guidelines”. Below, we outline specific safety evaluations conducted as part of the study protocol.

Monitoring for Worsening Depression and Suicidal Ideations or Behaviors

Participants will meet with a study clinician weekly during the treatment period. The interval medical history will be obtained and adverse events, changes to concomitant medications and dosing compliance will be recorded. Suicidal ideation and behavior will be specifically assessed, including a review of the Columbia Suicide Severity Rating Scale (C-SSRS) and the overall severity of symptoms will be monitored by the clinical global impression scale (CGI-S). If, at any point during the clinical trial, a participant will be assessed with a suicidal ideation with any intent or plan, as measured by a C-SSRS score of greater than 3 during the past week and/or with a CGI-S score ≥ 6 (indicating extreme illness severity) or a CGI-I score ≥ 6 (indicating an extreme worseness of the symptoms), the site PI, or his designee, will conduct a safety review to determine the appropriate course of action including whether acute intervention is needed and whether it is in the best interests of the subject to continue in the study.

Safety review: The safety review will consist of a separate review of safety and well-being of the participant by the site PI or his designee. This review will be documented by a Safety Review Form (SRF) that will be filed in the subject binder and that will consist of a brief description of the case and of the event that triggered the review. Outcome of the review will be the decision whether to continue or discontinue the subject from the protocol (if

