According to the ezogabine packaging information, physicians are advised to recommend that pregnant patients who took ezogabine enroll in the North American Antiepileptic Drug (NAAED) Pregnancy Registry. This can be done by calling the toll-free number [name], and must be done by patients themselves. Information on the registry can also be found at the website www.aedpregnancyregistry.org.

Suicidality

The careful monitoring of suicidal ideation (SI) and suicidal behavior is a critical component of any study conducted in patients with MDD as treatment emergent suicidal ideation has been associated with the use of antidepressants and other drugs with CNS penetration. A study clinician assesses SI, suicidal behavior, and risk at each study visit and a CSSRS is completed.

If, at any point during the clinical trial, a participant will be assessed with a suicidal ideation with any intent or plan, as measured by a C-SSRS score of greater than 3 during the past week and/or with a GCI-S score ≥ 6 (indicating extreme illness severity) or a CGI-I score ≥ 6 (indicating an extreme worseness of the symptoms), the site PI, or his designee, will

conduct a safety review to determine the appropriate course of action including whether acute intervention is needed and whether it is in the best interests of the subject to continue in the study. For more information refer to section 2.1 “Risk/Benefit Assessment” and 5.3 “Safety evaluations.”

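### At CGI-I ≥ 6, section 9.1.6 requires removal while section 5.3 leaves continuing to a site-PI review, and nothing states which rule governs

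*Protocol*

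**What the plan says.** **The consequence of CGI-I ≥ 6.** The CGI-I paragraph of protocol section 9.1.6 describes a 1 to 7 scale on which 6 is much worse and 7 very much worse. It then says that "subjects for whom the CGI-I is greater than 5 will be removed from the study", with care provided, and gives safety as the reason. No discretion is mentioned.

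Section 5.3 sends CGI-I ≥ 6 to a safety review by the site PI or a designee, recorded on a Safety Review Form. It states: "Outcome of the review will be the decision whether to continue or discontinue the subject from the protocol". Section 2.1 (Suicidality) and section 11.2.1 (Suicidality) give the same review rule. The C-SSRS paragraph of section 9.1.6, which follows the removal sentence directly, also orders a review when C-SSRS above 3 occurs with CGI-I ≥ 6. Part of its purpose is to decide "whether it is in the best interests of the subject to continue in the study".

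**The trigger for the review.** Section 5.3 has "C-SSRS score of greater than 3 during the past week and/or with a CGI-S score" of 6 or more, or CGI-I ≥ 6. Sections 2.1 and 11.2.1 use the same and/or construction. Section 9.1.6 (C-SSRS) and section 9.1.7 have instead "C-SSRS score of greater than 3 during the past week and with either a GCI-S score" of 6 or more, or CGI-I ≥ 6.

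**Cross-references.** Both section 9 paragraphs point to section 5.3 (in 9.1.6: "For more details regarding the safety review procedures, please refer to section 5.3"). Section 5.3 points back to section 9 for study procedures, and section 2.1 points to both.

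**The concern.** For the same rating, one rule fixes the outcome and the other leaves it open. The removal rule appears once, inside a scale description. The review of whether to continue appears in five places, including the section devoted to safety. Staff at one of the two sites could follow section 5.3 in good faith and keep a participant on blinded study drug whom section 9.1.6 takes out for safety, while the other site removes a participant with the same score.

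It would also be unclear whether keeping that participant is a protocol deviation. This matters because section 13 makes a major deviation with potential impact on participant safety reportable to the DSMB within 3 business days.

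On the trigger, a site working from section 9 could omit the PI review and its form for a participant with C-SSRS above 3 and no qualifying CGI score. The population is depressed, and section 2.1 itself reports a raised risk of suicidal thinking or behavior with antiepileptic drugs.

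**Working it through.** The plan gives no figure to reproduce here. The check is to set the rules side by side.

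**Step 1: do the two CGI-I rules cover the same scores?** The scale takes whole values 1 to 7 (section 9.1.6). Above 5 is {6, 7}, and ≥ 6 is {6, 7}. The sets are identical, so every participant under the removal rule is also under the section 5.3 review rule.

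**Step 2: what does each rule say for each combination?**

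| Finding at a visit | 2.1, 5.3, 11.2.1 (and/or) | 9.1.6 C-SSRS, 9.1.7 (and with either) | 9.1.6 CGI-I |
|---|---|---|---|
| C-SSRS > 3 only | Review | Not called for here | No removal rule |
| CGI-S ≥ 6 only | Review | Not called for here | No removal rule |
| CGI-I ≥ 6 only | Review; may continue | Not called for here | Removal |
| C-SSRS > 3 and CGI-S ≥ 6 | Review | Review | No removal rule |
| C-SSRS > 3 and CGI-I ≥ 6 | Review; may continue | Review of continuing | Removal |

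The last row shows that the tension does not depend on how and/or is read. Even under the narrower trigger, two adjacent paragraphs of section 9.1.6 send the same participant to removal and to a review of continuing.

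**Step 3: does another section settle it?**
- Section 12.1 says that treatment may be discontinued and lists possible reasons. No CGI-I threshold is among them.
- Section 10.3 lists CGI-I among the ratings at Visits 1 to 4 and attaches no consequence to a score.
- The cross-references between sections 5.3 and 9 run both ways, and neither section says that it prevails.
- Section 16 gives the SAP precedence for analyses only, and the SAP contains no CGI-I removal rule.

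**Step 4: is there a course that satisfies every passage?** Yes: hold the review, use it to settle acute care, then remove. For CGI-I ≥ 6 this takes away the option to continue that section 5.3 offers. No sentence says so.

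**Step 5: the CGI-S part of the trigger.** Inclusion criterion 5 requires CGI-S ≥ 4, and exclusion criterion 19 bars only scores above 6, that is 7. CGI-S = 6 is therefore eligible at entry. Under the and/or wording, such a participant would meet the review trigger at each visit without any change in condition.

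**The case against.** The strongest reply is that these are a general rule and a stricter specific one. The section 5.3 review serves three triggers, and its continue-or-discontinue outcome keeps its full meaning for C-SSRS above 3 or CGI-S ≥ 6 without CGI-I ≥ 6. Section 9.1.6 adds a tighter rule for one score. Section 5.3 sends its reader to section 9, so a site that stops at section 5.3 has not followed its own direction. This stands in part. A reader might infer that the two rules cannot both be obeyed, and the documents do not support that, because review followed by removal obeys both. What does not stand is that a site would know this. The pointer to section 9 is a general one for study procedures, and section 9 points back to section 5.3 for the review.

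On the trigger, a reader might infer that section 9 rules out a review for C-SSRS above 3 alone. It does not: neither paragraph says that the combination is the only trigger. Section 9.1.6 also requires assessment by the study psychiatrist for anyone with a plan or intent. This is inconsistent drafting, not a contradiction.

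A reader might also try to size the harm by the dose steps that a retained participant would still face. Those steps are the ordinary titration in section 8.4.1. They are subject to tolerability, do not arise on placebo, and are not linked by the documents to harm in such participants. They do not measure this defect.

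**Conclusion.** The point holds as an unresolved conflict between two stated safety rules for CGI-I scores of 6 and 7, with inconsistent trigger wording as a lesser matter. It should be fixed, because following section 5.3 as written can keep a participant whom section 9.1.6 removes. It rests on the text and on the scale having whole-number values.

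No size is claimed in participants, since neither document gives a rate for CGI-I ≥ 6. No effect on the primary analysis is claimed. A reader might infer one, because section 16.1 excludes patients without a follow-up scan and the rule applied could alter who has one. However, section 10.6 schedules the scan at early-withdrawal visits held before the primary outcome visit is complete, and the documents give nothing from which to estimate any remaining loss. Sample size, power and significance level are unaffected.

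**What to change.** **Consequence.** State in sections 5.3 and 12.1, with a cross-reference from 9.1.6, that CGI-I ≥ 6 leads to:
1. a documented site-PI review, to settle acute care;
2. no further dose increase;
3. removal with appropriate care;
4. taper by the dose-based schedule in section 10.5, unless safety requires an abrupt stop;
5. the section 10.6 early-withdrawal visit, with the scan if Visit 5 is not complete.

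Name section 10.5 explicitly. Section 2.1 speaks of at least 3 weeks, whereas section 10.5 gives two weeks from 750 mg, one week from 600 or 450 mg and none from 300 mg. Section 8.4.1 already sends early exits for intolerability to section 10.5.

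If the clinical team and the DSMB prefer PI discretion, amend the removal sentence in 9.1.6 instead. This is a clinical safety decision; either choice resolves the conflict if it is stated once.

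**Trigger.** Put one wording in section 5.3 and replace the text in 2.1, 9.1.6, 9.1.7 and 11.2.1 with a reference to it, so that C-SSRS above 3 alone always triggers the review. The clinical team should decide whether CGI-S ≥ 6 alone is a trigger, or only when it has worsened from baseline.

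**Cost.** One protocol amendment with prior written IRB and DSMB approval (section 18.1), and possibly some extra PI reviews.
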